1 SUMMARY

Title:	Short versus long interval to loop ileostomy reversal after ileal pouch surgery in patients with ulcerative colitis (SLIRPS) trial
Research Hypothesis:	In patients with ulcerative or indeterminate colitis who undergo ileal pouch anal anastomosis and diverting loop ileostomy (IPAA) surgery a short interval to loop ileostomy reversal will result in differences in complications and quality of life compared to a long interval to loop ileostomy reversal.
Phase:	III
Study design:	Prospective, randomized, multicenter
Study population:	Adult patients with ulcerative colitis (UC) or indeterminate colitis (IC) who will undergo ileal j-pouch surgery.
Sample size:	126-152 patients
Treatment:	
Phase 1:
 
 Colorectal excision, ileal j-pouch, & diverting ileostomy surgery 
Phase 2:
 
 Diverting ileostomy closure surgery
Treatment duration:	Phase 1 will have a treatment duration of approximately 6 weeks that will begin after informed consent #1 is obtained and will end within 1 week of ileal j-pouch surgery. Phase 2 will have a duration of approximately 6 months and will begin after informed consent #2 is obtained.
Criteria for inclusion:	
 Signed informed consents. Man or woman between 18 and 64 years of age. UC or IC diagnosed by routine clinical, radiographic, endoscopic, and pathological criteria. Patient will be scheduled for non-emergent proctocolectomy or completion proctectomy with ileal j-pouch anal anastomosis

Timing of Ileostomy Closure after Ileal Pouch Surgery

	
(IPAA) and loop ileostomy (IPAA).
 
 • Clinical assessment of patient after IPAA surgery indicates that patient is suitable for early ileostomy reversal
Criteria for exclusion:	
 • Age < 18 or > 64 years • Body mass index (BMI) equal or above 40 kg/m² • Crohn's disease or suspected Crohn's disease • Known previous or concurrent malignancy (other than that considered surgically cured, with no evidence for recurrence for 5 years). A recent history of basal cell or squamous cell carcinoma does not exclude the subject. • Pregnant patients and female patients who do not satisfy the standard of care requirements of participating centers for an elective surgical procedure. • Hemodynamic instability (persistent pulse rate < 50 or > 120 bpm, systolic blood pressure < 90 or > 160 mm Hg, uncontrolled cardiac arrhythmia, or active vasopressor drug use) • Systemic sepsis • Organ transplant recipient (e.g. Liver, Kidney, Pancreas) • Immunosuppression due to chemotherapy drug use or systemic disease. • Prednisone dose > 20 mg per day (or equivalent other steroid dose) within 4 weeks of scheduled IPAA • Patients with ongoing C. difficile colitis • Patients with pre-existing hepatic disease and portal hypertension • Patients with pre-existing renal dysfunction (creatinine >1.7 mg/dl) • Patients with poorly controlled pre-existing chronic lung disease • Therapeutic anticoagulation or coagulopathy (PTT or INR above normal range) • Blood Hemoglobin < 8 g/dl • Serum Albumin < 2.5 g/dl • Clinical assessment of patient after IPAA surgery indicates

Timing of Ileostomy Closure after Ileal Pouch Surgery

	
that patient is not suitable for early ileostomy reversal
 
 Participation in another clinical IBD drug trial within the last 30 days, or simultaneous participation in another clinical trial Well-founded doubt about the patient's cooperation Individualized decision by the surgeon to exclude the patient based on sound surgical judgment
Criteria for Evaluation:	A confirmed or presumed diagnosis of ulcerative or indeterminate/undetermined colitis will be determined by the study surgeons. The diagnosis will be based on the constellation of clinical, endoscopic, and pathology results that are used in routine practice to establish a diagnosis of these conditions.
Primary variables	Comprehensive Complication Index at 6 months after randomization.
Secondary variables:	(1) Total number of postoperative complications per patient; (2) Percent of patients with complications; (3) Total number of stoma related complications per patient; (4) Health-related quality of life; and (5) IPAA functional outcomes (all at 6 months after randomization).
Statistical analysis:	
A Consort Diagram will be used to account for all patients screened for inclusion in the trial; those who were excluded and included and reasons for exclusion; those who were randomized; and those who were followed at each time point or who were lost to follow-up. The primary analysis will be by intention-to-treat, meaning that the patients will be analyzed by the group to which they were randomized. This means that patients randomized to the short interval closure group who have postoperative complications that delay closure will still be analyzed in the group to which they were randomized. Secondary analyses will be done per-protocol (analyzing patients who followed the protocol), and as-treated (analyzing patients by the treatment they actually received).
 
Patient baseline characteristics will be compared between the early and late closure groups using a chi-square test for categorical variables and a t-test for independent samples for normal continuous variables or a Wilcoxon two sample ranks test for non-normal continuous variables.
 
Complications will be reported using the Clavien-Dindo classification. Perioperative details in the two groups will be compared using the same methods as were used for comparing the

Timing of Ileostomy Closure after Ileal Pouch Surgery

	
patient baseline characteristics.
 
The primary analysis will be comparing Comprehensive Complication index and overall complication rates up to 6 months postoperatively between the two randomized groups using a generalized linear model with a log-link function with group (short vs. long interval closure) and hospital as the independent variables. We will also include any patient baseline characteristics that remained unbalanced in spite of randomization. Secondary analyses will include a comparison of mean number of complications per patient using a zero-inflated Poisson model, and a comparison of severe complications (Clavien-Dindo Grade IIIa or higher) using the same methods as were used for the primary analysis. We will also compare the mean number of stoma related complications using a zero-inflated Poisson model. Since the quality of life scales are continuous variables measured over time, we will compare the early vs. late closure groups for these outcomes using linear mixed models.

Duration of study	Duration per patient will be approximately 7 months. The anticipated time of the overall study duration is approximately 18 months
Number of centres:	17-25 centers in United States

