A “defunctioning” loop ileostomy is routine to the practice of colorectal surgery. In general, this type of ileostomy is put in place to direct the enteric contents away from a newly created surgical anastomosis that is downstream (distal) to the ileostomy. For example, a defunctioning loop ileostomy is routinely made during ileal pouch anal anastomosis (IPAA) surgery to facilitate healing of the IPAA. It is common practice to leave the diverting ileostomy in place for 8 to 12 weeks with the idea that this interval is needed to ensure complete healing of the anastomosis. After 8 to 12 weeks, an imaging study (e.g. contrast enema) is performed to confirm complete healing of the anastomosis. After that, so long as healing of the anastomosis has occurred, the diverting ileostomy is surgically reversed. While potentially beneficial to the healing process, a diverting ileostomy may also be detrimental to the health and well-being of the patient. Potential detriments include dehydration, leakage from the ileostomy with resultant skin irritation and interference with activities of daily living, ileostomy dysfunction, and its negative impact on both physical and emotional function and quality of life. In an ideal situation, the diverting ileostomy would be left in place for an adequate period to facilitate healing of the anastomosis, while closing the ileostomy at the earliest appropriate time point in order to minimize the risks associated with an ileostomy.

The primary outcome variable for the study will be the Comprehensive Complication Index (CCI). The CCI is a novel continuous scale to measure surgical morbidity that has been developed in the past few years. (Slankamenac, 2013) It is based upon a survey of patients, nurses, and surgeons measuring their perceptions of the seriousness of 30 postoperative complications common in abdominal surgery (Slankamenac, 2011). From this survey, a score between 0 (no complications) and 100 (death) was developed to measure the occurrence of one or more

Timing of Ileostomy Closure after Ileal Pouch Surgery

postoperative complications in abdominal surgery patients, taking into account the number and seriousness of the complications. The score has been validated using four different methods (K. Slankamenac, 2013), and has been applied to the databases from 3 different randomized surgical trials and shown to be useful in reducing required sample sizes in surgical clinical trials (K. Slankamenac, 2014)

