Quality of life and functional outcomes of IPAA in patients with ulcerative colitis have been evaluated in retrospective studies. (Delaney 2003, Farouk 2000) The SF-12 is a validated quality of life measurement tool that has been used to evaluate patients who have undergone colorectal resection.

JUSTIFICATION AND OBJECTIVES OF THE CLINICAL TRIAL

Randomized prospective trials have evaluated the outcomes of standard (8 weeks) and decreased (8-13 day) intervals to defunctioning ileostomy reversal after rectal cancer surgery and have demonstrated superiority of decreased interval to closure. [Danielsen 2017; Alves 2008] The unique significance of our study is that it will focus on ulcerative colitis patients who undergo ileal pouch surgery with temporary defunctioning ileostomy.

This operation is performed on a minimum of 15 patients, with UC or IC, annually at University of Colorado Hospital and at the co-investigator centers. This surgery is performed by fellowship-trained and board certified colorectal surgeons at the University of Colorado.

Hypothesis: In patients with ulcerative or indeterminate colitis who undergo ileal pouch anal anastomosis and diverting loop ileostomy (IPAA) surgery* a short interval to loop ileostomy reversal will result in differences in complications and quality of life compared to a long interval to loop ileostomy reversal.

*For clarification, please see illustrations and images at end of this document

Aim #1: To compare the Comprehensive Complication Index (CCI), the incidence of postoperative complications, including total number of complications per patient, percent of patients with complications, and total number of ostomy-related complications per patient among IPAA patients who have their ileostomy reversed after a short interval compared to a long interval.

Aim #2: To compare the short vs. long interval groups on measures of health-related quality of life (SF-12) and IPAA functional outcomes

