7. PHASE 2 (day 7 to 12 or week 8-12): Ileostomy Closure:

- a. Early ileostomy closure will be performed at 7 to 12 days after IPAA.
- b. Late ileostomy closure will be performed 8 - 12 weeks after IPAA.
- c. The ileostomy closure surgical technique is at the discretion of the surgeon.
- d. CRF-5 (ileostomy reversal details) will be completed within 3 days of ileostomy reversal surgery.
- e. Endoscopic examination (optional): Rigid and/or flexible endoscopic examination of the IPAA may be performed per standard practice/standard of care, including non-study-related informed consent, at the discretion of the study surgeon following standard of care. (CRF-5)

8. PHASE 2 (day 7 – 12 to 6 months): Outcome assessment:

- a. The Comprehensive Complication Index and postoperative complications will be assessed and recorded by the study surgeon or trial assistant after review of the medical record, conversation with patient, and members of the care team (when appropriate). This assessment and documentation will begin immediately after randomization is performed and will be updated at 1-2 month intervals until 6 months after randomization. (CRF-6)
- b. Functional outcomes and quality of life (CRF-7): IPAA functional outcomes and quality of life (SF-12) will be assessed and recorded once at 6 months after ostomy reversal.

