10 STATISTICAL CONSIDERATIONS

Sample Size Calculation

The developers of the CCI consider a 10-point difference in their 0 to 100 morbidity scale to be clinically meaningful; it reflects a 1-grade difference in the established Clavien-Dindo classification of postoperative complications (Slankamenac, 2014; Clavien, 2009). They also report a standard deviation of the CCI of 20-22 in two surgical trials. Assuming 80% power and an $\alpha = 0.05$ level of significance, our trial would need about 63-76 patients per group, or a total of 126-152 patients to complete both phases of the trial. It is anticipated that up to 600 patients will be required for phase 1 due to the expected $\leq 75\%$ drop out of phase 1 patients who are not eligible for phase 2.

Statistical analyses

A Consort Diagram will be used to account for all patients screened for inclusion in the trial; those who were excluded and included and reasons for exclusion; those who were randomized; and those who were followed at each time point or who were lost to follow-up. The primary analysis will be by intention-to-treat, meaning that the patients will be analyzed by the group to which they were randomized. This means that patients randomized to the short interval closure group who have postoperative complications that delay closure will still be analyzed in the group to which they were randomized. Secondary analyses will be done per-protocol (analyzing patients who followed the protocol), and as-treated (analyzing patients by the treatment they actually received).

Patient baseline characteristics will be compared between the early and late closure groups using a chi-square test for categorical variables and a t-test for independent samples for normal continuous variables or a Wilcoxon two sample ranks test for non-normal continuous variables.

Complications will be reported using the Clavien-Dindo classification. Perioperative details in the two groups will be compared using the same methods as were used for comparing the patient baseline characteristics.

The primary analysis will be comparing Comprehensive Complication index and overall complication rates up to 6 months postoperatively between the two randomized groups using a generalized linear model with a log-link function with

Timing of Ileostomy Closure after Ileal Pouch Surgery

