Functional outcome and SF-12 Case Report Form (CRF)-7 completion (Function & SF-12)	PHASE 2: At 6 months after randomization	REDCap application / surgeon or assistant
Case Report Form (CRF)-8 completion (Adverse Events)	PHASE 2: Assessed on a daily interval, during hospitalization(s), after IPAA and ostomy reversal surgery and then reassessed at 1-2 month intervals, until 6 months after IPAA.	REDCap application / surgeon or assistant

Clinical Adverse Event Reporting Form

Short versus long interval to loop ileostomy reversal after ileal pouch surgery in patients with ulcerative colitis (SLIRPS) trial

A randomized, prospective trial investigating the timing of diverting ileostomy closure after ileal j-pouch surgery.

Event ID: _____ Study Center: _____ Study ID: _____

Event Name: _____

DOB: ____ / ____ / ____-____ Gender: _____ Race: _____
mm dd yyyy

Name of MD Reporting Event?	_____
Date of Medical Review	____ / ____ / ____-____ mm dd yyyy
Is this a Serious Adverse Event (SAE)?	 Yes  No
Indicate all classifications(s) applicable	 Death  Life threatening  Disability  Congenital anomaly/birth defect  Hospitalization - Initial  Hospitalization - Prolongation  Other
Specify Other	_____
Relationship/Causality (likelihood that study agent caused the event)	 Not related  Probably not related  Possibly related  Related

Timing of Ileostomy Closure after Ileal Pouch Surgery

	Is the event Expected?
	Is the event Unexpected?

Timing of Ileostomy Closure after Ileal Pouch Surgery

MD Narrative:	

Measures at the onset of adverse event
 
 None
 
 Surgical Procedure
 
 Treatment with medication  Other
	
Specify Other:	

Outcome of event (sequelae are defined as conditions following and resulting from event)
 
 Recovered without sequelae
 
 Recovered with sequelae
 
 Not yet recovered
 
 Died
	
Signature of Study Center MD	
Date Form Completed	____ / ____ / ____ - ____ mm dd yyyy

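### Pouch function is compared by randomized arm, but no rule covers a patient with an ileostomy at the assessment, so by default the comparison is conditional on a working pouch

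*Combined protocol and SAP*

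**What the plan says.** **Endpoint and comparison.** The Summary (Section 1, Secondary variables) ends its list with "5) IPAA functional outcomes (all at 6 months after randomization". Aim #2 in Section 2 is "To compare the short vs. long interval groups on measures of health-related quality of life (SF-12) and IPAA functional outcomes".

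**Timing.** The Appendix timeline has a row "Functional outcome and SF-12 Case Report Form (CRF)-7 completion (Function & SF-12" with the timing "PHASE 2: At 6 months after randomization". Section 3, step 8b, says instead that function and SF-12 "will be assessed and recorded once at 6 months after ostomy reversal".

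**Diversion and closure.** Section 2 describes the ileostomy as "put in place to direct the enteric contents away from a newly created surgical anastomosis". It also describes usual practice as conditional: "so long as healing of the anastomosis has occurred, the diverting ileostomy is surgically reversed". The late arm closes at 8 to 12 weeks in step 7b of Section 3, but at 8 weeks or later with no upper limit in step 6 and in the Appendix timeline.

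**Analysis.** Section 10 makes the primary analysis intention-to-treat and adds, for delayed closure: "patients randomized to the short interval closure group who have postoperative complications that delay closure will still be analyzed in the group", meaning the assigned one. Per-protocol and as-treated analyses are secondary. Linear mixed models are given for the quality of life scales. No instrument, model or missing-data rule is given for pouch function.

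**The concern.** Pouch function can be observed only when bowel content passes through the pouch. The plan expects complications that delay closure. Section 5 lists clinical leak, abscess, stenosis and unplanned reoperation as expected events, and any of these could leave a patient diverted, or diverted again, when function is due. The intention-to-treat text says which group such a patient belongs to. It does not say what value the patient contributes to an outcome that cannot be observed.

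With no rule, an analyst will use the scores that exist. The comparison is then among patients with a working pouch, and closure timing may influence who is in that set. If the arms differ in the share still or again diverted, the function result does not show it, and a reader could take a conditional result for one that covers everyone randomized.

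**Working it through.** **1. The plan's own figure.** The only sample size stated is for the Comprehensive Complication Index: difference 10, SD 20-22, 80% power, alpha 0.05 (Section 10). With n per group = 2 × (1.960 + 0.842)² × SD² / 10², SD 20 gives 62.8, so 63, and SD 22 gives 76.0, so 76. Totals are 126 and 152, as stated. This point does not change them. No figure is stated for function.

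**2. The two clocks, side by side.**
- Six months after randomization (Summary, Appendix timeline): every randomized patient has an assessment date. SF-12 can be completed with a stoma, but function cannot be scored in a diverted patient.
- Six months after reversal (Section 3, step 8b): a patient whose closure is only delayed is scored normally. A patient never reversed has no date, so neither function nor SF-12 is due. A patient diverted again has a date but no score for function.

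The gap exists under both, but different patients fall into it.

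**3. What else the plan records.** CRF-5 records the closure operation. Unplanned reoperation within 6 months of IPAA is a defined complication in Section 5, but re-diversion is not named. Complications are followed until 6 months after randomization. Taking 6 months as 183 days and randomization on day 5-12, that ends at day 188-195 after IPAA. On the reversal clock with closure at 8-12 weeks, late-arm function is due at day 56 + 183 = 239 to 84 + 183 = 267. A re-diversion between those dates would fall outside complication follow-up.

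**4. How many patients.** The documents give no rate, so these are assumptions.

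| Diverted at assessment | Unscored of 63 | Unscored of 76 |
|---|---|---|
| 2% | 1.3 | 1.5 |
| 5% | 3.2 | 3.8 |
| 10% | 6.3 | 7.6 |
| 15% | 9.4 | 11.4 |

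**5. How much could be hidden.** Assume equal function among patients with a working pouch, and count a diverted patient as 2 SD below their mean. The scored-only difference is then 0 by construction. The difference over all randomized patients is 2 SD × (p_early − p_late):
- 5% vs 2%: 2 × 0.03 = 0.06 SD
- 10% vs 3%: 2 × 0.07 = 0.14 SD
- 15% vs 5%: 2 × 0.10 = 0.20 SD

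Swapping the rates between arms reverses the sign. Equal rates give 0.

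**6. The same on a rank scale.** Place diverted patients worst, with ties counted half. The probability that an early-arm patient does better is (1 − p_early)(1 − p_late)/2 + (1 − p_early) × p_late + p_early × p_late/2, which simplifies to 0.5 + (p_late − p_early)/2. At 10% vs 5% this is 0.475, at 15% vs 5% it is 0.45, at 5% vs 10% it is 0.525, and at equal rates it is 0.50. The scored-only value is 0.50 throughout.

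**The case against.** A reader might infer that the plan excludes diverted patients, or that it breaks its own intention-to-treat rule. The documents do not support either reading. On the randomization clock no text excludes anyone; restriction to scorable patients is what happens when no rule exists. Intention-to-treat is attached to the primary analysis. The content of CRF-7 is not shown, so a stoma-status item may already be on it.

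A reader might also infer that the arm with more failures will look better on function. That is not shown. The calculation fixes function as equal among scorable patients, and its rates, its 2 SD penalty and the placing of more failures in the early arm are all chosen.

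Further points against the concern carry weight. Leak, abscess, stenosis and reoperation still count in the Comprehensive Complication Index and the complication endpoints. Clinically unsuitable patients and those with a radiologic leak are screened out before randomization, which may keep diversion rare. A delay in closure does not imply diversion at 6 months. Even a 0.20 SD difference is small for this trial: with 63-76 per arm, power is Φ(0.20 × √(n/2) − 1.96), or about 20-23%, against a design effect of 10/22 to 10/20 = 0.45-0.50 SD. Worst-rank scoring also assumes that any diverted patient is worse off than any patient with a poorly working pouch, which the documents do not establish.

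These points limit the size of the problem and rule out imposing a worst-rank analysis as the main comparison. They do not fill the gap. No endpoint reports how many patients in each arm have a pouch in continuity, and the complication endpoints do not tell a reader of the function result who is absent from it.

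**Conclusion.** The concern holds in a limited form and should be acted on as a cheap improvement to a secondary endpoint. Function is compared by randomized arm with no rule or companion endpoint for patients who have an ileostomy at the assessment. Under step 8b of Section 3, a patient never reversed has no function or SF-12 assessment.

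The default result therefore describes patients with a working pouch and should be read that way. The size and direction of any bias are unknown. The range of 0.06-0.20 SD rests on assumed diversion of 2-15%, unequal rates and a 2 SD penalty, and it vanishes if the rates are equal. The primary endpoint and the sample size are unaffected.

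**What to change.** 1. Reconcile step 8b of Section 3 with the Summary and the Appendix timeline on one assessment clock that exists for every randomized patient. A clock that starts at reversal does not.
2. Record on CRF-7, for every randomized patient, whether the pouch is in continuity at the assessment (stoma closed and not diverted again). If the form already has this item, say so in the protocol.
3. In the Summary and Section 10, report the percent in continuity by arm, by intention-to-treat, beside the function result, and label the function scores as conditional on continuity.
4. State that SF-12 is collected regardless of stoma status.
5. Optionally, pre-specify a rank-based sensitivity analysis that places patients without continuity worst, with stated handling of deaths and losses to follow-up. It need not be the main comparison.

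The function instrument and its analysis model should be named in the same edit, since the conditional label has to attach to a defined score. The rule should be fixed before outcomes by arm are seen.

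Cost: one extra CRF field, one extra reported line and a few sentences in the plan.
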